The GH Method defines in detail the strategy and objectives for each day of exercise, including intensity levels, duration, muscle groups, order of exercises, repetitions, speed, breaks, techniques to enhance the effectiveness, along with an accompanying educational curriculum and psychological strategy correlated with the workout program. The detailed workouts are then customized to the individual patient based on the assessments of strength, recuperation, energy among others that are constantly updated throughout the program. The GH Method is organized into Levels and all patients begin in Level 0. For the purposes of this study, patients will experience at least 12 months of the GH Method which may incorporate the following levels:

Level 0. This level comprises approximately 8 separate weeks although many of the weeks may be repeated depending on the needs of a particular patient. The major physical objective of Level 0 is to effectively engage their muscle fiber (without much breakdown) to activate their innate strength, endurance and cardiovascular capacity. Before the end of Level 0, we measure patient strength, endurance, and cardiovascular capacity to ensure we can train patients to their optimum recuperation level. The major educational objective of this Level is to teach clients the technical form and self-awareness that is mandatory before they can proceed to the next Level. The major psychological objective of this Level is to establish a safe and caring environment for patients, to reframe how they think about exercise and their health, and for us to become experts in all aspects of the patient.

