1. Counseling twice weekly on diet and nutrition will improve food choices to more healthy choices of fresh fruits and vegetables and low fat protein sources. To test this hypothesis, patients will undergo a food frequency questionnaire at baseline to document choices prior to intervention. A food frequency questionnaire will be performed at the end of the intervention to determine the effect of counseling on protein source, number of calories, and frequency of fresh fruits and vegetables. Counseling will consist of the diabetes prevention program counseling which is a well-established, well-verified intervention, commonly accepted as an effective means of providing a standardized nutritional education.

2. The combination of exercise and dietary intervention positively affects body composition. With this hypothesis we will test whether muscle strength (Biodex measurements) and muscle mass (DEXA scan) changes after 12 months of an exercise intervention. We hypothesize that the transplant itself will not affect activity levels, strength levels or muscle mass. Baseline measurement will be performed before the intervention, at 6 months post intervention, and the final measurement would be taken at 12 months with muscle mass measured by DEXA and strength measured again by Biodex.

3. Patients receiving strength training will have significantly higher activity levels when compared with no intervention or physical therapy. The rationale for this hypothesis is that patients without strength training will fail to increase muscle mass and strength and this inability will translate to persistently lower activity levels than those patients with strength training. Once again levels will be documented with an accelerometer and PROMIS questionnaires, 6 months and 12months to document the effect of intervention. In addition, if patients in the control group and GH group decide to

have the optional muscle biopsy, it will help evaluate how targeted exercise may change muscle development measuring expression of mature microRNAs using total RNA extraction.

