4. Patients with strength training will activate type II macrophages which are anti-inflammatory and pro-regenerative, tipping the balance away from inflammation towards regeneration when compared to the other treatment groups. Since strength training is likely to initiate signals of muscle regeneration, and since type II macrophages play a key role in this effect, it is possible that increasing the signaling to the muscle for regeneration may also increase the proportion of active type II macrophages which are anti-inflammatory. To test this hypothesis, we will test the proportion of peripheral blood M1/M2 macrophages at baseline, 6 months and 12 months after the initiation of the intervention. Recognizing that immunosuppression may significantly confound this proportion and overall suppress it, we will also test circulating levels of pro-inflammatory cytokines such as C-reactive protein(CRP), IL-6, IL-1, TNF-alpha, homocysteine, adiponectin, leptin, and resistin as well as pro-regenerative cytokines such as TGF-beta and IL-10.

5. We expect patients with strength training will experience less renal dysfunction, decreased hemoglobin A1C, increased peripheral vascular function, decreased fasting blood sugar when compared to the other treatment groups. The rationale for this hypothesis is the finding that muscle mass provides active regulation of glucose and other metabolites. Therefore increasing this may provide improved metabolic function. These laboratory panels are part of the standard transplant follow-up labs and add no cost to the project.

6. Patients with strength training will have an overall improved sense of well-being and energy level compared to those with physical therapy or no treatment. With twice weekly counseling for activity and nutrition, patients will be asked about their general health, mental health and pain intensity using the PROMIS questionnaires.

METHODS

Setting: The study will include 225 patients, to achieve a goal of 180 patients in the GH study group and 45 patients in the control group. Every patient will be followed for 3 years after the start of the intervention. Patients will start the intervention at least 2 months post-transplant; however they can be enrolled prior to transplant.

Main Study Inclusion criteria:

- Successful kidney transplantation (KTx) with primary graft function
- Age between 18 and 65 years

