- Adequate cognitive ability to complete the questionnaires, give consent for the study and follow the physical and diet instructions

Main Study Exclusion criteria:

- transplant of any other organ besides kidney alone or a combination of a kidney/pancreas

- non-ambulatory or significant orthopedic problems
- cardiac/pulmonary disease that contraindicate the physical training
- any contraindication to exercise testing per the American Heart Association
- unable to comply with the training program

Muscle Biopsy Inclusion:

- Age between 18 and 65 years
- Patients who have a brachial–cephalic arteriovenous fistula (AVF) in the elbow or brachial–basilic AVF in the arm
- Exercise Arm- the biopsy will only be performed once, after the 12 month exercise intervention is completed (which will be longer than 1 year post transplant surgery)
- Control Arm- this procedure will be performed once, around one year post transplant surgery (may occur at any time during the study)

Muscle Biopsy Exclusion:

- Patients that do not meet the inclusion criteria

Identifying potential subjects for recruitment:

A waiver for an alteration of consent and waiver of documentation of consent is being requested for review of medical records to identify potential patients for study recruitment and also for a telephone screening process for patients that response to a recruitment flyer. The principal investigator already has access to these records as part of daily care for all patients seen in clinic. This presents no more than minimal risk since this data will be kept confidential.

Moreover, as part of the telephone screening process for patients interested in this study there will be oral consent obtained to start the screening process in order to determine if the patients are eligible to be in the study. If the patients are eligible, they will be schedule for a visit where they will be consented to be in the study.

Randomization: All patients who meet the enrollment criteria will be randomized 4:1 to the GH group or the control group.

- GH group: patients will be treated for 12 months with the GH method (Appendix 1) for one hour twice a week

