Maximal aerobic capacity test (VO₂ max): For subjects over 55 yrs or that are classified as moderate to high risk according to ACSM's risk stratification scale, this will occur in the presence of a physician. We will use a modified Balke Treadmill protocol: the treadmill will be set at a constant speed (3.3 mph) while the incline is increased by 2% every two minutes. This protocol is selected to ensure that the elderly subjects will be able to perform a maximal aerobic test. For younger (18-35 yr) subjects, the test will begin at a 10% grade and increase 2% every 2 minutes. If maximal effort is not reached

by minute 10 and a 20% grade, speed will be increased by 0.3 mph until maximal effort is achieved.

Accelerometer: subjects will be given an accelerometer with instructions for use and be asked to wear it around their waist for 1 week while awake to measure their level of physical activity. This will be completed at baseline, 6 months and 12 months post-intervention.

Muscle Biopsy

Optional muscle biopsies for GH group and control group, will be performed to measure expression of mature microRNAs using total RNA extraction, which will help evaluate how targeted exercise may change muscle development. The muscle biopsy will be performed by [name], [name], [name], and/or [name], all of which are experienced surgeons with prior experience performing muscle biopsies. The muscle biopsy will be performed at the University of Illinois at Chicago Outpatient Clinic, with an address at [name].

Prior to kidney transplantation many patients undergo hemodialysis treatments to sustain life. Hemodialysis is a process of purifying the blood of a person whose kidneys are not working normally. Arteriovenous fistula provides an access route for hemodialysis to be possible, by providing a direct connection of an artery to a vein. As part of standard of care at UIC, the AV fistula is ligated (a surgical procedure of closing off a blood vessel) at around one year post-transplant. As a way to retrieve bicep muscle biopsy samples we will retrieve samples during the closing AV fistulas (ligation) in kidney transplant patients with stable renal function. Patients will be consented with a supplemental consent for the bicep muscle biopsy.

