reporting done via the Lifestyle Inventory, understand their eating and sleeping patterns in greater detail by eliminating their opinions and emotional relationship and just focusing on actual intake, and provide a tool for ongoing monitoring and an opportunity for increasing patient's self-reflection on their food and sleeping habits. This will only be administered to the GH patients. Importantly, this is not a measurement tool that we would give at a specific time during the study; it is being used during the study by the research personnel and GH Method personnel to help manage self-reported behavior changes with the patients.

Counseling

Patients in the both arms will be counseled regarding weight loss per standard of care which consists of a pre-transplant and a post-transplant nutrition evaluation and education.

Video recording (optional)

Video recordings will be an option on the consent form for patients that are randomized into the GH exercise group. The option to be video recorded by the GH team at the beginning and end of the patient's 12 months of training. The recordings will be used to compare the progress of the patient from the beginning and end of GH training.

GH Study Visits:

At least one week prior to the first GH session with a patient, the written assessments will be completed and returned to GH personnel for scoring and processing. The first four GH sessions (over 2 weeks) for any patient will be 75 minutes. Following the first 4 sessions, ongoing patients will be slotted into recurring 60 minute time slots for the remaining 50 weeks. All of these visits will occur in the UIC Disability Health and Social Policy Building (DHSP) located at [name] in Suites 158, 190, and 195. The procedure visits at baseline, 6 and 12 months will take 2-3 hours.

At least twice per week, GH personnel will attempt to follow-up with patients via text message, email or a phone call to evaluate their physical recuperation and overall health and energy or to track their performance with a behavior change goal.

Patients will be asked to complete a physical regimen based on the following:

Summary of GH Study Visits:

- Patients may be asked to repeat previous weeks and/or skip a particular week depending on their energy, progress, and overall health.

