Week 13	Cardio Exercises (e.g. run in place). 7 different exercises are done as one round and three rounds total.	Moderate	2 - 3minutes

Week 14	1 Set of 12 - 16 Repetitions	Moderate	2 minutes
Week 15	3 Sets of declining heaviness with 8, 10 and 12 repetitions	Moderate	3 minutes
Week 16	3 Exercises in Each Set and 7 sets	Moderate	3 minutes
Week 17	1 Set 90 Seconds	Moderate/Light	3 minutes
Week 18	Cardio Exercises (e.g. run in place). 3 different exercises per set. 3 Sets equal one Round. Three Rounds total	Light	2 minutes
Week 19	1 Warm-Up Set of 12 repetitions 1 Set of 7 Repetitions	Moderate/Heavy	3 Minutes
Week 20	1 Set of 25 - 30 Repetitions	Moderate	3 Minutes
Week 21	1 st Set: Warm up of 12 repetitions. 2 nd Set: 6 repetitions	Moderate/Heavy	3 minutes
Week 22	1 Set: 35 - 40 repetitions	Moderate/Light	3 minutes
Week 23	1 Warm Up Set: 15 repetitions 1 Heavier Set 8 - 10 repetitions	Moderate/Heavy	3 minutes
Week 24	1 Set of 90 Seconds focused on resistance	Moderate	3 minutes
Week 25	Cardio Exercises. 10 exercises in a set. 2 Sets.	Moderate	3 minutes
Week 26	3 Exercises in 1 Set. 9 Sets.	Moderate	3 minutes
Week 27	1 Warm Up Set: 8 – 12 reps. 1 Heavy Set: 8 – 12 reps. Slower Speed.	Moderate/Heavy	2 minutes
Week 28	1 Warm Up Set 8 reps 1 Heavy Set 8 reps. Medium speed.	Heavy	3 minutes
Week 29	3 Sets on each exercise of 6, 8, 12 repetitions. Lower weights each set. Medium speed.	Moderate	3 minutes
Week 30	1 set 90 seconds. Medium speed.	Lighter	2 minutes
Week 31	1 Warm Up Set: 8 – 12 reps. 1 Heavy Set: 8 – 12 reps. Slower Speed.	Moderate/Heavy	2 minutes
Week 32	3 Sets on each exercise of 6, 8, 12 repetitions. Lower weights each set. Medium speed.	Moderate	3 minutes
Week 33	1 set 90 seconds. Medium speed.	Lighter	2 minutes
Week 34	1 Warm Up Set: 8 – 12 reps. 1 Heavy Set: 8 – 12 reps. Slower Speed.	Moderate/Heavy	2 minutes
Week 35	3 Sets on each exercise of 6, 8, 12 repetitions. Lower weights each set. Medium speed.	Moderate	3 minutes

Week 36	1 set 90 seconds. Medium speed.	Lighter	2 minutes
Week 37	1 Warm Up Set: 8 – 12 reps. 1 Heavy Set: 8 – 12 reps. Slower Speed.	Moderate/Heavy	2 minutes
Week 38	2 Sets Per Exercise without break between: 18 reps and 16 reps	Moderate/Light	2 minutes
Week 39	3 Sets on each exercise of 6, 8, 12 repetitions. Lower weights each set. Medium speed.	Moderate	3 minutes
Week 40	1 set 90 seconds focused on resistance. Medium speed.	Lighter	2 minutes
Week 41	Cardio Exercises. 10 exercises in a set. 2 Sets.	Moderate	3 minutes

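### The 6-month accelerometer week, and possibly the 12-month one, includes supervised GH sessions that only one arm attends, so total activity mixes attendance with the carry-over behind Hypothesis 3

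*Combined protocol and SAP*

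**What the plan says.** **Device.** The Accelerometer paragraph, under Body composition and strength, says subjects will "be asked to wear it around their waist for 1 week while awake to measure their level of physical activity". It sets this at baseline, 6 and 12 months. It does not mention training sessions, define the outcome (counts, steps or minutes) or give a visit window.

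**Hypothesis.** Hypothesis 3 predicts higher activity levels with strength training. Its rationale is that untrained patients fail to gain muscle mass and strength, and "this inability will translate to persistently lower activity levels than those patients with strength training". The measurement sentence reads: "Once again levels will be documented with an accelerometer and PROMIS questionnaires, 6 months and 12months to document the effect of intervention".

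**Programme.** Under Randomization, GH "patients will be treated for 12 months with the GH method (Appendix 1) for one hour twice a week". GH Study Visits gives four longer sessions over the first 2 weeks, after which "ongoing patients will be slotted into recurring 60 minute time slots for the remaining 50 weeks". Controls receive standard care and are offered GH only after their final control visit.

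**Analysis.** The Statistical analyses section lists five efficacy criteria: well-being, lean/fat ratio, BMI, inflammatory parameters and metabolic parameters. Its between-group tests are for those. Activity level is not among them.

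**The concern.** The rationale of Hypothesis 3 concerns what training does to the rest of a patient's activity. A device worn through all waking hours of a programme week also records the training itself, and it does so in one arm only. A GH patient whose activity outside sessions had not changed would still contribute a higher total than before.

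A positive accelerometer result could then reflect strength carried over into daily life, attendance at the sessions, or both, and the plan collects nothing that would tell these apart. After month 12, activity is assessed only by telephone, so no later device measurement would settle the matter.

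**Working it through.** **1. Plan's own figures.** 180 + 45 = 225 and 180/45 = 4, which agrees with 4:1 randomization. 2 + 50 = 52 programme weeks, which agrees with the 52-row table. The documents give no SD, effect size or power for the accelerometer, so there is no planned figure to reproduce for this outcome.

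**2. Which clock.** The Accelerometer paragraph counts its 6 and 12 months as post-intervention. Hypothesis 4 uses the fuller wording "at baseline, 6 months and 12 months after the initiation of the intervention", and Body composition and strength treats 12 months as the end of the study. Counting from the start of GH is the reading that fits.

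**3. Where the wear weeks fall.** Programme week k covers days 7(k − 1) + 1 to 7k. Six months is 365.25/2 = day 182.6 and twelve months is day 365.25.

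| Visit | Wear week ends at visit | Wear week starts after visit |
|---|---|---|
| 6 months | week 26 (days 176–182) | week 27 (days 183–189) |
| 12 months | about week 52 (days 358–364) | week 53, after the nominal last session |

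Both 6-month options lie inside the 52 weeks. The 12-month option depends on a window that the plan does not set. The GH description also says that "patients will experience at least 12 months of the GH Method", so a patient could still be attending after day 364.

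**4. What sessions add.** 2 × 60 = 120 minutes a week in GH and 0 in controls. As a share of waking time this is small: 2/(7 × 18) = 1.6% to 2/(7 × 14) = 2.0%, assuming 14 to 18 waking hours a day. As a share of active minutes it could be larger, but the documents give neither the usual level of activity nor how much of a session a waist device would register.

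**5. Illustration only.** Suppose there is no carry-over and sessions add b recorded minutes a week, with between-patient SD s. The standardized difference is d = b/s. Its standard error is √(1/45 + 1/180) = 0.1667, so the noncentrality is d/0.1667 on 223 degrees of freedom. All values of b and s below are assumptions.

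| b (min/week) | s (min/week) | d | d/0.1667 | Chance of p < 0.05, two-sided |
|---|---|---|---|---|
| 30 | 300 | 0.10 | 0.60 | 9% |
| 30 | 160 | 0.19 | 1.14 | 21% |
| 30 | 100 | 0.30 | 1.80 | 43% |
| 60 | 200 | 0.30 | 1.80 | 43% |
| 60 | 100 | 0.60 | 3.60 | 95% |

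The nominal rate is 5%. If session time is removed alike in both arms, the difference built in by the sessions is 0 and the rate returns to 5%.

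**The case against.** **Total activity is a legitimate outcome.** Hypothesis 3, read literally, speaks of activity levels, and the Background names low activity and poor uptake of exercise as the problem. This stands as a reason to keep reporting the total. It does not make the total a test of the stated rationale.

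**The contribution may be small.** Most sessions are machine or bench work with breaks of 2 to 3 minutes, which a waist device may barely register. This stands too, and it is why no single size is claimed.

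**Other measures exist.** PROMIS is also named for Hypothesis 3, and telephone follow-up asks about activity every 6 months for 2 years after the programme. Both are self-report. The telephone calls do bear on persistence, but neither separates session time in the device record.

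**Stronger readings that the documents do not support.**
- A reader might infer that the wear weeks coincide with cardio weeks. The rows for weeks 25 and 52 do read "Cardio Exercises. 10 exercises in a set. 2 Sets", but the nominal 6-month wear week is strength week 26 or 27, and weeks may be repeated or skipped. The example of running in place belongs to weeks 6, 13 and 18. The point needs none of this, since every programme week has two exercise days.
- A reader might infer that neither visit can answer the question. At 12 months the wear week may follow the last session; the fault there is an unset window.
- A reader might infer that the trial's efficacy conclusion is biased. Activity is outside the five criteria, and the t-test in the illustration is not one the plan specifies for it.

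**Conclusion.** The point holds for Hypothesis 3. At 6 months the overlap is certain for every GH patient still attending; at 12 months it is possible. Recorded session movement can only add to the GH total, so this component favours GH. Its size cannot be computed from the documents. The rejection rates of 9% to 95% shown above depend wholly on the assumed minutes and SDs, on a two-sided test, and on full numbers of 180 and 45. They show that the effect could matter, not that it will.

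The five efficacy criteria are untouched. This is a worthwhile correction to a secondary question, not a flaw in the trial's main comparison.

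**What to change.** 1. State that the 6- and 12-month visits count from the start of the intervention, and define the accelerometer outcome and what counts as valid wear.
2. Record the actual date and time of each GH session in the wear week. The recurring slots give scheduled times, but attendance needs its own log.
3. Make activity outside sessions the Hypothesis 3 accelerometer measure, expressed per valid wear hour or day. Mask matched weekday and time blocks, or the same days, in controls. Masking in GH alone would leave unequal wear time and unmatched days.
4. Place the 12-month wear week in the first full week after the last GH session. Place it at the same time from start in controls, before any control patient takes up the offer of GH.
5. Report total activity, including sessions, alongside.

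This uses the existing device and visits. It costs a session log and a data-processing rule, slightly less analysable wear time, a small shift in the 12-month timing, and possibly a less favourable GH figure. A wear week just after the programme shows early carry-over only; longer persistence would still rest on the telephone follow-up.

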In the upper extremities, the typical sites for muscle biopsy are deltoid or biceps. We want to focus on the bicep muscle only and we will include only patients with brachial–cephalic AVF in the elbow or brachial–basilic AVF in the arm will be selected in order to have easily access to the biceps muscle.

The skin incision for closing brachial–cephalic or brachial–basilic AV fistula in the upper extremity is made over the area of the arteriovenous anastomosis: in the elbow for brachial–cephalic AVF or in the arm for brachial–basilic AVF.

After shaving and disinfection of the external part of the surgical site, local subcutaneous anaesthesia is achieved using 4 mL of lidocaine (2%) with special attention to ensure that no lidocaine is injected in the muscle. Thus, injection of lidocaine is done superficially and obliquely.

In case of voluminous fistula, a regional anesthesia via peripheral nerve block is preferred. In these cases, the anesthetic (a mix of lidocaine and ropivacaine) is injected by anesthesiologist near the brachial plexus to block sensations of pain from a specific area of the body. Nerve blocks usually last longer than local anesthesia.

A small cutaneous incision (about 4-5 cm) is made in the antecubital fossa, over the area of the arteriovenous anastomosis, following the medial border of the biceps muscle. The muscle is retracted slightly laterally in order to allow access to the thin aponeurotic sheath which contains the neuro-vascular bundle. Biceps brachii muscle is visualized and cut. Muscle fibres are carefully dissected in their longitudinal axis away from the tendon insertion, to obtain a sample of 300 mg. This is about the size of 2-3 grains of rice. Both ends are immediately clipped and hemostasis is controlled. The bundle is fixed on a cork support at its apparent resting length.

The skin incision is closed with 3.0 Nylon suture and pressure is applied to the incision site.

This procedure will be done once at 12 months for patients randomized to the exercise arm (after the exercise intervention is completed) and once at any time during the 12 month study duration for the control arm as long as the patient is at least one year post transplant.

Status of systemic inflammation

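### The exercise-arm biopsy cannot come before month 14 after transplant, yet its only occasion is a fistula closure done at around one year, so samples come from training completers with late or deferred closure

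*Combined protocol and SAP*

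**What the plan says.** The relevant statements are spread over four places in the combined protocol and SAP.

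- **Start of training (METHODS, Setting):** "Patients will start the intervention at least 2 months post-transplant; however they can be enrolled prior to transplant". No latest start is given.
- **Length of training (Randomization):** in the GH group, "patients will be treated for 12 months with the GH method (Appendix 1) for one hour twice a week".
- **GH biopsy timing:** the Muscle Biopsy Inclusion list says "the biopsy will only be performed once, after the 12 month exercise intervention is completed (which will be longer than 1 year post transplant surgery". The procedure text at the end of the Muscle Biopsy section agrees: "This procedure will be done once at 12 months for patients randomized to the exercise arm (after the exercise intervention is completed".
- **Occasion of the biopsy (Muscle Biopsy section):** under standard care at the site, "the AV fistula is ligated (a surgical procedure of closing off a blood vessel) at around one year post-transplant", and "we will retrieve samples during the closing AV fistulas (ligation) in kidney transplant patients with stable renal function". No other sampling route is described. The inclusion list requires one of two named fistula types, and the incision described is the one used to close the fistula.

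For controls, the inclusion list places the biopsy at about one year after transplant, at any point in the study. The procedure text allows it at any point in the 12-month study once a year has passed since transplant.

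The stated purpose, in Hypothesis 3 and again in the Muscle Biopsy section, is to learn from muscle microRNA how the exercise programme affects muscle development.

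**The concern.** The biopsy has no appointment of its own; it depends on an operation whose usual date is set by standard care. In the GH arm the biopsy rule points to a date later than that operation's usual date. In the control arm the two roughly coincide. The visible text does not say whether closure is deferred for GH patients in the sub-study, whether tissue can be taken separately, or what happens if the fistula is already closed when training ends.

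What is at stake is the meaning of the microRNA comparison. If closure keeps to its usual timing, GH samples come only from patients who finished training and whose fistula happened to be closed late. If closure is deferred in the GH arm, surgical timing depends on allocation among those who opt in. In both cases the groups compared differ in more than exercise. A deferral would also mean that some GH patients have an open fistula at the 12-month vascular and cardiac tests when comparable controls do not.

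**Working it through.** **Inputs**

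- Start of training: month s after transplant, s ≥ 2 (Setting).
- Length of training: 12 months (Randomization).
- GH biopsy: only after training ends (Muscle Biopsy Inclusion; Muscle Biopsy section).
- Usual closure: around month 12, with the spread not stated (Muscle Biopsy section).
- Control biopsy: within the 12-month study and at least 12 months after transplant (Muscle Biopsy section).

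**Step 1: earliest GH biopsy.** Months after transplant = s + 12. With s = 2 this is 2 + 12 = 14. The plan's own figure, later than one year after transplant, is reproduced: 14 > 12.

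**Step 2: lag behind a month-12 closure.** Counting from transplant, (s + 12) − 12 = s months. Counting from the start of training, closure falls at 12 − s and the biopsy at 12, so the gap is again 12 − (12 − s) = s. The minimum is 2 months.

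**Step 3: control window.** It runs from the later of 12 and s to s + 12.

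| Start s (month after transplant) | Earliest GH biopsy (s + 12) | Months after a month-12 closure | Control window |
|---|---|---|---|
| 2 | 14 | 2 | 12 to 14 |
| 3 | 15 | 3 | 12 to 15 |
| 4 | 16 | 4 | 12 to 16 |
| 6 | 18 | 6 | 12 to 18 |
| 9 | 21 | 9 | 12 to 21 |
| 12 | 24 | 12 | 12 to 24 |
| 15 | 27 | 15 | 15 to 27 |

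For every start up to month 12, the control window opens at month 12, while the GH window opens at s + 12, where the control window ends.

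**Step 4: how loosely must the closure date be read?** Assume that usual closure falls within 12 ± w months. A GH patient can be biopsied at a usual-time closure only if s + 12 ≤ 12 + w, that is s ≤ w. With s ≥ 2:

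- w below 2: no compatible start.
- w = 2: only a start at month 2.
- w = 3: starts at months 2 to 3.
- w = 4: starts at months 2 to 4.
- w = 6: starts at months 2 to 6.

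Even for compatible starts, closure must fall late in its range. With w = 3 and s = 2, it must fall between months 14 and 15 of a range from 9 to 15.

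**The case against.** The strongest reply is that the timing word is elastic and the authors knew that the GH biopsy would come late, since the inclusion list says so. Both points stand. A reader might infer that no GH patient on the standard schedule can supply a sample. The documents do not support that as a fact: it holds only if the spread around one year is less than 2 months either way, and the plan gives no spread.

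A second reply is that controls do not fit perfectly either. This is also right. The procedure text excludes a control whose fistula is closed before month 12. A control who starts after month 12 also needs a fistula still open past the usual date. Control sampling may run to s + 12, so some controls can be sampled as late as GH patients. The difference between arms is in when sampling can begin, and it is clear only for starts up to about month 12.

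Third, a reader might infer that surgery is being postponed for research in the GH arm, or that the 12-month vascular and cardiac results are biased. Neither is shown. The visible text is silent on deferral, and the supplemental biopsy consent, which might address it, was not available for this review. Any effect on the vascular or cardiac tests depends on deferral, would be limited to patients who opt in with an eligible fistula, and cannot be sized from the documents.

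Finally, the sub-study is optional and exploratory, with no stated sample size. That limits the weight of the point. It does not restore the exercise interpretation that the protocol gives to the comparison.

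**Conclusion.** The concern holds for the biopsy sub-study. Under the stated rules the GH biopsy falls at month 14 after transplant or later, at least 2 months after a month-12 closure and s months after it for a start at month s. GH samples therefore come from training completers with late or deferred closure, whereas controls who start by about month 12 can be sampled from about month 12. Completion, closure timing and time since transplant are mixed with exercise, so a microRNA difference could not be attributed to exercise alone.

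This rests on two readings: that closure is the only sampling occasion, which is all the text describes, and that around one year has a limited spread. Only a spread of several months would accommodate more than the earliest starters.

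The point does not reach the main efficacy analysis: the five criteria under Statistical analyses do not name the biopsy.

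**What to change.** 1. Reconcile the Setting, Randomization, Muscle Biopsy Inclusion and Muscle Biopsy texts so that they state how the GH biopsy relates to the timing of fistula closure, and what happens if closure comes before training ends. This review takes no position on which timing is right.
2. Record in both arms the closure date, months since transplant at biopsy, and whether the fistula is open or closed at each visit. Report these by arm.
3. Report the microRNA comparison as descriptive, in the selected patients actually biopsied, with time since transplant shown by arm. Remove the claim in Hypothesis 3 and the Muscle Biopsy section that it evaluates an exercise effect on muscle development.
4. If closure timing turns out to differ by arm, show fistula status beside the 12-month vascular and cardiac results and use it only in a sensitivity analysis. Keep the unadjusted randomised comparison as the main one: fistula status arises after randomisation and may be affected by allocation, so adjusting for it could itself bias the comparison.

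The cost is a protocol clarification, in substance one extra data field (the closure date, from which the other items largely follow), and a narrower sub-study claim. The sensitivity analysis, if needed, would have to be specified, because the plan lists only t-tests and chi-square or Fisher tests. No extra procedure is required.
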